4.2 Discontinuation of Treatment and/or Subject Withdrawal

4.2.1 Reasons for Discontinuation of Treatment and/or Subject Withdrawal

Subjects may discontinue treatment with investigational product or withdraw from the study at any time at their own request, or at the discretion of the investigator or CSL for safety, behavioral or administrative reasons (eg, due to an AE, protocol deviation, loss to follow-up, subject noncompliance, study termination).

In accordance with International Council for Harmonisation (ICH) principles of Good Clinical Practice (GCP), the investigator always has the option to advise a subject to withdraw from the study if the subject's safety or well-being is compromised by his or her further participation in the study. Concern for the interests of the subject must always prevail over the interests of the study.

The investigator should record in the electronic case report form (eCRF) and in the subject's medical records the reason and date of subject withdrawal or discontinuation of treatment with investigational product.

4.2.2 Procedures for Handling Withdrawals

If a subject declines further participation or is withdrawn from the study, attempts will be made to complete and document the assessments scheduled as described in [Section 8.5.8](#).

If the subject is withdrawn from the study after receiving Investigational Product, every effort will be made to ensure that the relevant safety assessments are completed. The subject may also be asked by the investigator to complete other study assessments.

If a subject discontinues treatment with investigational product but remains in the study, they should complete follow-up assessments as detailed in the Schedule of Assessments.

If the subject withdraws from the study, and also withdraws consent for disclosure of future information, CSL may retain and continue to use any data collected before such withdrawal of consent. CSL may also continue to collect the subject's allograft function and survival information from the study site, with the subject's consent.

4.2.3 Replacement Policy

Subjects withdrawn from the study following randomization will not be replaced.

5 Study Interventions

5.1 Description of Investigational Product(s)

5.1.1 C1-esterase Inhibitor, Human (500 IU/mL)

Table 11 Description of C1-INH

Substance name	C1-esterase Inhibitor, Human (500 IU/mL)
Active substance	C1-esterase inhibitor
Trade name	Not applicable
Dosage form	Lyophilized powder for reconstitution; 1500 IU C1-INH per single-use vial.
Dose	60 IU/kg
Mode of administration	Intravenous/subcutaneous injection

C1-esterase Inhibitor, Human (500 IU/mL) will be manufactured by CSL in accordance with ICH Good Manufacturing Practice guidelines and local regulatory requirements.

Before use, each vial of C1-INH is reconstituted with 3 mL water for injection. 60 IU/kg C1-INH is equivalent to a volume of 0.12 mL/kg.

Instructions for reconstitution are presented in the Investigational Medicinal Product Handling Instructions.

The dose of C1-INH will be based on the body weight obtained with vital signs assessment at the Screening Visit, and will not be changed throughout the study. The actual dose of C1-INH will be rounded to the lowest 500 IU, as this corresponds with a practical volume of 1 mL of C1-INH. Refer to the Investigational Medicinal Product Handling Instructions.

5.1.2 Placebo

Table 12 Description of Placebo

Substance name	placebo
Substance	Excipients of C1-INH plus albumin
Trade name	Not applicable
Dosage form	Lyophilized powder for reconstitution
Dose	0.12 mL/kg
Mode of administration	Subcutaneous injection

Placebo will be manufactured by CSL in accordance with ICH Good Manufacturing Practice guidelines and local regulatory requirements.

Before use, each vial of placebo is reconstituted with 3 mL water for injection.

Instructions for reconstitution are presented in the Investigational Medicinal Product Handling Instructions.

The volume of placebo will be based on the body weight obtained with vital signs assessment at the Screening Visit, and will not be changed through the study. The actual dose of placebo will be rounded to the lowest 1 mL as if the subject receiving C1-INH.

5.2 Packaging, Labeling, Supply and Storage

5.2.1 Packaging and Labeling

The investigational products will be packaged and labeled according to current ICH Good Manufacturing Practice and GCP guidelines, and national legal requirements.

The investigational product used in TP1 (ie, C1-INH only) will be packaged in a way to make it visually distinct from the investigational product used in TP2 (ie, C1-INH or placebo).

5.2.2 Supply and Storage

The investigational product will be supplied to the study sites by CSL or delegate.

The investigational product must be stored under temperature-controlled and monitored conditions at the predefined temperature range in a secure storage area as specified in the site Investigational Product Handling Instructions.

5.2.3 Direct to Patient

Investigational product may be shipped directly to the subject's home in those countries where it is acceptable. To ensure proper patient data confidentiality a dedicated process with a special courier service will be implemented.

5.3 Accountability and Destruction

The investigational product must be used only as directed in the clinical study protocol.

The investigator (or delegate) will confirm receipt of all shipments of investigational product in the interactive response technology (IRT).

All supplies of investigational product must be accounted for throughout the study.

Records for the delivery of investigational product to the study site, the inventory at the study site, the use by each subject, and the destruction or return of investigational product to CSL/designee must be maintained by the investigator (or delegate) using the appropriate form or IRT.

The investigator (or delegate) must provide reasons for any discrepancies in drug accountability.

Used and partially used vials of investigational product will be collected, as applicable. Any unused, partially used, or empty vials of investigational product should not be destroyed until the drug accountability documentation or institution specific destruction procedure has been checked by the study monitor. Any destruction of investigational product must be documented and provided to CSL.

All drug accountability records must be stored in the site file and must be readily available for inspection by the study monitor and/or auditor, and open to regulatory inspection at any time.

Further details regarding accountability and destruction of investigational product are provided in the site Investigational Product Handling Instructions.

5.4 Other Intervention(s)

5.4.1 Intravenous Immunoglobulin

During the open-label TP1, IVIg will be administered every 4 weeks at a dose of 2 grams/kg. The dose must be administered over a minimum period of at least 2 days, and may be administered over a period of up to 5 days. The administration of IVIg will begin on Study Day 1 with the following exceptions:

1. For subjects who have received their last dose of IVIg < 1 gram/kg as part of standard of care within the 2 weeks before Study Day 1 OR
2. For subjects who have received their last dose of IVIg ≥ 1 gram/kg as part of standard of care within the 4 weeks before Study Day 1

For these subjects, the administration of IVIg will begin on the Week 4 Visit.

During TP2 and Retreatment Period, IVIg may be administered if $DSA \geq 2000$ mean fluorescence intensity (MFI) based on the clinical judgement of the investigator.

The complete schedules for IVIg dosing during TP1, TP2, and any Retreatment Period are presented in [Table 1](#), [Table 2](#), and [Table 5](#), respectively.

All blood draws scheduled for the same visit as IVIg dosing should be taken BEFORE the initiation of IVIg dosing.

If a scheduled dose of IV C1-INH is the same day as IVIg administration, it should be administered AFTER the IVIg dose. Subcutaneous C1-INH may be administered during an IVIg infusion.

5.4.2 Plasmapheresis

Donor-specific antibodies will be measured in both the central and local laboratories (see [Section 8.1.3.5](#)). Central laboratory results will be used for analyses. Local laboratory results will be used by the investigator in addition to other clinical findings to make treatment decisions, including the initiation of plasmapheresis.

Plasmapheresis should be performed if a subject has DSA with clinical significance based on the PI's medical judgement.

The timing and duration of plasmapheresis should occur as per the local standard of care and be documented in the eCRF. The use of any replacement fluid should also be documented.

If blood draws for laboratory testing (including PK samples) are scheduled at the same visit as plasmapheresis, blood samples should be taken BEFORE plasmapheresis.

If a scheduled dose of C1-INH is the same day as plasmapheresis, it should be administered AFTER plasmapheresis.

If plasmapheresis occurs during a scheduled IVIg administration, administration of IVIg should be postponed until the plasmapheresis session is complete.

Donor-specific antibodies should be tested in the local laboratory within between 24 and 72 hours after completing plasmapheresis.

If the strongest DSA does not decrease by $\geq 50\%$ of pre-plasmapheresis MFI, then plasmapheresis may be repeated, at the discretion of the investigator.

5.5 Dose Modification

Modifications of the C1-INH dose (ie, dose increase or dose decrease) are not permitted during the study.

6 Allocation, Dosing, and Administration

6.1 Allocation to Treatment

6.1.1 Subject Assignment

After providing written informed consent, the subject will be issued with a study-level unique subject identification number. The subject identification number will be used to identify the subject for the duration of the study. Subject identification numbers will not be reassigned or reused.

6.1.2 Randomization Procedures

All subjects will receive open-label C1-INH during TP1. Subjects who are eligible for TP2 (ie, responder subjects, as defined in [Section 8.1.3.2](#)) will be assigned to either continued C1-INH or matched placebo in accordance with a computer-generated randomization list. Investigational product assigned in TP2 will be allocated on a 1:1 ratio. The randomization (permuted block) will be stratified on the following factors:

- DSA: sensitized prior to transplantation versus de novo; de novo is defined as the development of DSA after transplantation. In the case of both sensitized and de novo, the subject will be considered sensitized for stratification purposes.
- AMR severity: severe versus non-severe (ie, all other severities); severe is defined as new onset oliguria (<400 cc/24 hours) or anuria with the current episode of AMR.

Treatment assignment will be determined centrally. The randomization list will be generated and managed by the study's IRT external service provider. A detailed user guide for the IRT will be available.

6.1.3 Blinding Procedures

Treatment Period 1 is open-label.

Treatment Period 2 is double-blind. The blind will be maintained during TP2 for investigational site staff, including investigators, and subjects, and CSL.

The blind will be maintained for investigational site staff, including investigators, and subjects during the Responder Follow-up Period, and any Retreatment Periods.

6.1.3.1 Blinding Method

Vials of investigational product (ie, either C1-INH or placebo) will be packaged identically and individual packages may be identified only by the kit number.

Investigational product vials will be fully covered to avoid visual inspection of the contents by the subjects and study personnel. A standard procedure will be followed to completely reconstitute the lyophilized product to make up the solution. The solution will then be withdrawn through a filter and will be inspected in the syringe prior to administration. C1-INH or placebo will be administered in a blinded manner.

A dose of 60 IU/kg C1-INH is equivalent to a volume of 0.12 mL/kg. In order to maintain the blind in TP2, the same volume of investigational product (ie, 0.12 mL/kg, rounded to the lowest mL) will be administered to all subjects regardless of treatment assignment.

6.1.3.2 Breaking the Blind for an Emergency

In emergency situations involving the safety of the subject, the Investigator may break the blind using the IRT system. The reason for unblinding the randomization code must be fully

documented. Emergency unblinding will be performed using the IRT. Steps for navigating the IRT for emergency unblinding are defined in the IRT Manual.

6.2 Dosing and Administration

A description of the dose and dosing regimen of the investigational product can be found in [Section 3.2](#).

A description of the investigational product can be found in [Section 5.1](#).

6.3 Treatment Compliance

Treatment compliance will be assessed using data captured in the eCRF including the date and time of the injection of investigational product (C1-INH or placebo) and the volume of investigational product that is administered.

7 Contraindications, Permitted Therapies, and Prohibited Therapies

7.1 Contraindications and Precautions to Further Dosing

The investigational product is contraindicated in individuals who have manifested severe immediate hypersensitivity reactions, including anaphylaxis to C1-INH, albumin, or to any of the excipients of the investigational product (ie, C1-INH or placebo).

7.2 Permitted Therapies

The following therapies are PERMITTED during the study (note, this list is not intended to be all inclusive):

- Maintenance immune suppression, steroid therapy, and anti-lymphocyte therapy licensed for clinical use, unless specifically prohibited in Section 7.3.
- Prophylactic antibacterial, antifungal, and antiviral agents.
- Prescribed medication(s) required for the management of chronic medical conditions.
- Over the counter medications and dietary supplements.
- Plasmapheresis, as described in [Section 5.4.2](#).

7.3 Prohibited Therapies

The following therapies are NOT PERMITTED during TP1, TP2, and the Retreatment Period:

- Other C1-esterase inhibitor products (eg, Berlinert, Cinryze).
- Other complement inhibitors, including eculizumab.
- Proteasome inhibitors, including but not limited to bortezomib, carfilzomib, and ixazomib.
- Any immune suppression agent used to treat AMR that is not licensed for clinical use.
- Administration of any other investigational agent during the study.

Subjects are not to be enrolled into the study if they receive any prohibited therapy or any therapy in a prohibited dosage that cannot be discontinued or reduced to a permitted dose before enrollment.

If administration of any prohibited therapy becomes necessary during the study for medical reasons, the subject may be withdrawn from further study participation.

Subjects are not permitted to receive any prohibited therapies between the time of signing informed consent and the time of completing participation in the study.

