10.3.3.1 Primary Efficacy Analysis

The primary analysis of the primary efficacy endpoint of loss-of-response at the End-of-TP2, will be based on a logistic regression model. The randomized treatment groups, C1-INH and placebo, will be compared based on the logistic model.

Subjects will be considered to have lost response if they drop-out or are lost to follow-up before the response status at the End-of-TP2 could be determined.

If π is the probability that an individual in a given treatment group will have a loss-of-response at the End-of-TP2, the logistic model assumes that in each treatment group, binary outcome of response status can be described by a model which assumes independence between subjects. Also, the model assumes that all subjects with the same covariate values have the same probability, such that the logit of π is a linear function of the regression coefficients particular to that individual:

$$\text{Logit}(\pi) = \log(\pi/(1-\pi)) = \alpha + \beta_T X_T,$$

where X_T is the indicator variable for treatment (C1-INH=1, placebo = 0).

Please note the stratification factors for randomization are not included in this model as difference in efficacy is not expected based on these strata. However, subjects have been randomized based on these strata of DSA sensitized versus DSA de novo and AMR severity (severe versus all other severities) to ensure balance among these strata.

The odds ratio for C1-INH versus placebo is $\exp(\beta_T)$ based on this model for primary efficacy analysis. The primary hypothesis to be tested is $H_0: \beta_T = 0$ vs $H_1: \beta_T \neq 0$. This will be tested using the Wald statistic derived from maximum likelihood estimation of the logistic model. If this hypothesis is rejected at the 0.05 level of significance and the point estimate of β_T is positive, efficacy will be declared. The logistic model will be used to provide point estimates of the odds ratio and risk difference, with 95% confidence intervals by treatment groups. Summary statistics of proportion of subjects with loss-of-response will also be presented by treatment. If maximum likelihood estimation of the logistic model fails to converge then exact methods for logistic regression will be used for hypothesis and estimation.

Components of loss-of-response at the End-of-TP2 will be summarized by treatment groups in terms of the proportion of subjects with:

- End-of-TP2 eGFR (mean of Week 36 and Week 38 eGFR values) that is not stable, defined as:

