13.4 Protocol Deviations

All instances where the requirements of the study protocol were not complied with will be tracked. Corresponding subjects may be withdrawn from the study at the discretion of the investigator and/or CSL. Study protocol deviations arise when either subjects who have been entered in the study and/or the study sites deviate from the IEC/IRB-approved study protocol.

If a major protocol deviation (ie, a deviation that could have a significant effect on the subject's safety, rights, or welfare and/or on the integrity of the study data) occurs, the investigator must notify CSL and the appropriate IRB/IEC as soon as possible or as per local requirements.

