8.1.1 Imputation of Non-Date Missing Data

Non-date Clinical Data

All available data will be analyzed using suitable statistical methods. For analysis of percent responders, all subjects in the appropriate analysis set (ITT Analysis Set or mITT Analysis Set) will be included in the denominator when calculating the percentages; any subject who drops out of the study at any time after randomization will be defined for the purpose of analysis as a non-responder.

Subjects with the designation of treatment relationship for adverse events (AEs) and serious adverse events (SAEs) missing will have the worst case assumed to impute the relationship: if relationship to study treatment is missing it will be assumed to be “Yes”.

In summaries of absolute values and change from baseline, subjects with missing baseline values will not be included in baseline rows or in the change from baseline summary statistics.

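### The protocol permits a randomized subject to be withdrawn from the study itself for a prohibited therapy or a protocol deviation, which can impute a primary-endpoint loss and leave the 48-month graft outcome missing

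*Protocol*

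**What the plan says.** Three sections of the protocol allow a randomized subject to leave the study by someone else's decision.

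- Section 7.3, on prohibited therapies: "If administration of any prohibited therapy becomes necessary during the study for medical reasons, the subject may be withdrawn from further study participation".
- Section 13.4, on protocol deviations: "Corresponding subjects may be withdrawn from the study at the discretion of the investigator and/or CSL".
- Section 4.2.1, on stopping treatment or leaving the study in general: "at the discretion of the investigator or CSL for safety, behavioral or administrative reasons". Protocol deviation and noncompliance are among its examples.

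Section 4.2.2 offers another route: "If a subject discontinues treatment with investigational product but remains in the study, they should complete follow-up assessments". It also lets the sponsor go on collecting "allograft function and survival information from the study site" after withdrawal, but as an option and with the subject's consent. Withdrawn randomized subjects are not replaced (4.2.3).

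Two scoring rules apply to the primary endpoint. Protocol 10.3.3.1, repeated in SAP 10.1, reads "Subjects will be considered to have lost response if they drop-out or are lost to follow-up"; the sentence then limits this to subjects who leave while their End-of-TP2 status is still undetermined. SAP 8.1.1 has no such limit: "any subject who drops out of the study at any time after randomization will be defined for the purpose of analysis as a non-responder".

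For all-cause allograft failure at 48 months, Protocol 10.3.3.2 reuses the primary logistic model and states no rule for a missing outcome. Section 10.1.2 only expects few losses to follow-up.

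**The concern.** Nothing says when 7.3, 13.4 or 4.2.1 applies rather than the 4.2.2 route of stopping product and staying in follow-up. A sponsor or investigator decision can therefore become a primary event in a subject whose graft was stable. The planned outputs would not show it. The component tables in Protocol 10.3.3.1 and SAP 10.1 list unstable eGFR, allograft failure and death, with no line for losses imputed because of withdrawal. The sensitivity analysis in 10.3.3.1 adds covariates and does not address withdrawals.

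At 48 months the same decision can leave graft status unknown for an endpoint that Protocol 10.3 places in the alpha-protected hierarchy. This loss is avoidable: 10.1.2 itself notes that standard of care keeps these patients under close follow-up.

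**Working it through.** **Inputs.** Loss-of-response 0.75 on placebo and 0.30 on C1-INH, 30 per arm, two-sided alpha 0.05, stated power about 95% (Protocol 10.1.1). Allograft failure at 48 months 0.75 and 0.25, from survival of 0.25 and 0.75 (10.1.2). The withdrawal rate is not in the documents; 0 to 20% per arm is my assumption.

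**The plan's own figure.** Pooled-variance chi-square power is Φ{[d√n − 1.96√(2p̄(1−p̄))] / √(p₀(1−p₀)+p₁(1−p₁))}. With d = 0.45, n = 30, p̄ = 0.525:

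(0.45×5.477 − 1.96×0.706)/0.630 = 1.71, so power = 95.7%.

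The likelihood-ratio approximation gives 94.5%. The stated 95% is reproduced.

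**Primary endpoint with withdrawals counted as losses.** If a share w of an arm is withdrawn independently of outcome, p′ = p + w(1−p). For w = 0.10 in both arms: 0.30 + 0.10×0.70 = 0.370 and 0.75 + 0.10×0.25 = 0.775.

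| Withdrawn (C1-INH / placebo) | Loss (C1-INH / placebo) | Difference | Power |
|---|---|---|---|
| 0 / 0 | 0.300 / 0.750 | 0.450 | 95.7% |
| 5% / 5% | 0.335 / 0.763 | 0.428 | 93.5% |
| 10% / 10% | 0.370 / 0.775 | 0.405 | 90.8% |
| 20% / 20% | 0.440 / 0.800 | 0.360 | 83.7% |
| 0 / 20% | 0.300 / 0.800 | 0.500 | 98.7% |
| 20% / 0 | 0.440 / 0.750 | 0.310 | 69.6% |

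The last two rows bracket the direction: withdrawal on placebo alone widens the difference, withdrawal on C1-INH alone narrows it. Had every withdrawn subject lost response anyway, p′ = p and nothing changes. Had the subject been stable, each withdrawal adds 1/30 = 3.3 points to that arm.

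**48 months, analysing only known outcomes.** Expected failures are 0.25×30 = 7.5 and 0.75×30 = 22.5. Suppose k grafts that would have failed go unobserved (k is assumed):

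- none: 0.25 vs 0.75, difference 0.50;
- 3 on placebo: 19.5/27 = 0.722, difference 0.472;
- 6 on placebo: 16.5/24 = 0.688, difference 0.438, power 92% by exact enumeration of the likelihood-ratio test, against 98.5% with none missing;
- 6 in each arm: 1.5/24 = 0.063 vs 0.688, difference 0.625.

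Failure is understated in every arm that loses such grafts, but the treatment difference can shrink or grow.

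**The two drop-out rules.** A subject withdrawn after a Week 36 creatinine has a determinable status, because SAP 8.2.9 accepts one of the Week 36 and Week 38 values if the other is missing. Protocol 10.3.3.1 and SAP 10.1 would then score the observed eGFR, while SAP 8.1.1 would score a failure. Read literally, SAP 8.1.1 would also override an observed Week 38 result for a subject who drops out in follow-up.

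**Periods covered by 7.3.** The prohibited list is headed as applying to TP1, TP2 and the Retreatment Period. The withdrawal sentence speaks of the study, and the last sentence runs from consent to the end of participation. Subjects in Responder Follow-up receive local standard of care (1.3). Whether a prohibited agent given then falls under 7.3 cannot be settled from the text.

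**What remains under the final SAP.** Thirteen subjects were randomized (SAP 3). If they split 6 and 7 (an assumption), one imputed loss in an otherwise stable subject moves an arm's proportion by 1/7 = 14 to 1/6 = 17 points. The mITT set may be smaller.

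**The case against.** The other side has real points, and they rule out three stronger readings.

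*A reader might infer that any TP2 withdrawal is a loss whatever the eGFR.* Protocol 10.3.3.1 says so only when End-of-TP2 status could not be determined, and 8.5.8.2 asks for every effort to do the Week 38 assessments at withdrawal. Only SAP 8.1.1 supports the unconditional reading, and it conflicts with SAP 10.1. The documents do not say whether an early creatinine taken at withdrawal counts as the Week 38 value, so an early withdrawal may still be undeterminable.

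*A reader might infer that withdrawal takes the highest-risk grafts out of the 48-month comparison.* Withdrawal is discretionary, graft and survival data may still be collected with consent, and 8.5.8.4 asks for Month 48 assessments at withdrawal, although those record status on that day rather than at Month 48. The prohibited list is also narrow: complement inhibitors, proteasome inhibitors, and unlicensed or investigational agents. Steroids, anti-lymphocyte therapy, plasmapheresis and, under conditions, IVIg remain available. Need for a prohibited agent may mark a failing graft; a deviation need not.

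*A reader might infer a bias in favour of C1-INH.* Site staff and subjects are blinded in TP2 and follow-up (6.1.3), no withdrawal rate by arm is given, and the scenarios move both ways.

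Counting need for a prohibited rejection therapy as failure could also be a deliberate composite strategy. The documents do not state it as one, and it would not justify counting a deviation-based withdrawal as a loss.

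What survives is that study-level withdrawal is permitted for these reasons, its scoring is inconsistent, and the 48-month model has no missing-outcome rule.

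**Conclusion.** The point holds as a risk that the plan creates and could cheaply avoid. It is not an established bias. Discretionary withdrawal can produce imputed primary events and missing graft outcomes. With equal withdrawal in both arms, independent of outcome and counted as loss, primary power falls to 90.8% at 10% and 83.7% at 20%. Both rates are assumptions, and the effect is nil if the withdrawn subjects would have lost response anyway. The direction of any bias in the treatment difference cannot be determined from the documents.

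The power and 48-month results apply to the protocol as planned. The final SAP drops formal testing (4.2.1.3, 7.3) and the 48-month analyses (5, 10.2, 10.3). What is still affected is the descriptive loss-of-response proportion and its confidence interval in SAP 10.1, where a single imputed loss carries much weight.

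**What to change.** 1. In Protocol 4.2.1, 7.3 and 13.4, state that a prohibited therapy or a protocol deviation does not end study participation. The subject stays in scheduled creatinine, graft-status and survival follow-up to Week 38 and Month 48 unless consent is withdrawn, and the therapy or deviation is recorded. All three sections need the change, since 4.2.1 alone would preserve the discretion. Whether investigational product continues is a separate clinical decision.
2. Score the primary endpoint from observed eGFR, graft status and survival where available. Reconcile SAP 8.1.1 with Protocol 10.3.3.1 and SAP 10.1 so that one drop-out rule remains.
3. Add a line to the component table for losses imputed because of withdrawal, by arm and reason. This can still be done for the terminated study's report.
4. Reconcile the sentences in 7.3 on which periods the prohibition covers.
5. Were the 48-month analysis to be run, give 10.3.3.2 a missing-outcome rule and a sensitivity analysis.

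The cost is a few sentences of amendment and SAP text, one table row, and a few more contacts that are already on the schedule.
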